6.5 Overdose

An overdose is defined as the accidental or intentional administration of any dose of a product that is considered both excessive and medically important. All occurrences of overdose must be reported as an SAE (see Section 6.1.1 for reporting details.).

6.6 Potential Drug Induced Liver Injury (DILI)

Specific criteria for identifying potential DILI have not been identified for this protocol. Standard medical practice in identifying and monitoring hepatic issues should be followed.

Potential drug induced liver injury is defined as:

- AT (ALT or AST) elevation > 3 times upper limit of normal (ULN) AND
- Total bilirubin > 2 times ULN, without initial findings of cholestasis (elevated serum alkaline phosphatase)
 AND
- 3) No other immediately apparent possible causes of AT elevation and hyperbilirubinemia, including, but not limited to, viral hepatitis, pre-existing chronic or acute liver disease, or the administration of other drug(s) known to be hepatotoxic.

Wherever possible, timely confirmation of initial liver-related laboratory abnormalities should occur prior to the reporting of a potential DILI event. All occurrences of potential DILIs, meeting the defined criteria, must be reported as SAEs (see Section 6.1.1 for reporting details).

6.7 Other Safety Considerations

Any significant worsening noted during interim or final physical examinations, electrocardiogram, x-ray filming, any other potential safety assessment required or not required by protocol should also be recorded as a nonserious or serious AE, as appropriate, and reported accordingly.

7. DATA MONITORING COMMITTEE AND OTHER EXTERNAL COMMITTEES

Not applicable

8. STATISTICAL CONSIDERATIONS

Descriptive statistics (n, mean, median, and standard deviation; minimum, maximum or interquartile range) will be provided for the safety analysis and by subgroups based on types of prior therapy and line of therapy (2L/3L) groups. Because the sample size for the study is small, summary statistics with their associated 95% confidence intervals and tests of hypotheses will be based, to the extent possible, using small-sample statistics like the Clopper-Pearson for binomial data. Median time-to-event and its 95% confidence interval will be based on the Kaplan-Meier (KM) estimation procedure. The KM curves will be presented for time-to-event endpoints.

8.1 Sample Size Determination

8.1.1 EPd Cohort

Seventy-two subjects will be screened with approximately 17% projected to fail screening. This total number is based on logistical consideration with statistical properties outlined below. Screening will continue until a minimum of 60 subjects are enrolled and treated.

Under the assumptions that:

- time to PFS is exponentially distributed
- median time of PFS is 11 months for subjects treated with pomalidomide + dexamethasone and will increase to median of 15 months with the addition of elotuzumab to the treatment mix
- an increase of 4 months in median corresponds to relative risk ratio of 0.73 (0.0462 monthly risk in the elotuzumab add-on and 0.0630 monthly historical risk in the pomalidomide + dexamethasone treated-subjects)

Sixty subjects enrolled over a 24-month period are sufficient to detect an increase in median from 11 to 15 months with about 70% power in a one-sided test with a 0.05 significance level.

Assuming a monthly hazard rate of 0.0462, 48 of the 60 treated subjects are **expected** to have PFS events over a 24-month follow up period.

Power is calculated using PASS12 using the one-sample exponential module where the median is mapped to mean by dividing the assumed alternative median by logarithm of 2. The calculated power and event counts are consistent with power and event counts based on one sample log rank test where the number of events is calculated assuming relative risk ratio of 0.73.

8.1.2 EN Cohort

The planned sample size will be approximately 30 treated subjects; screening will continue until a minimum of 30 patients are enrolled and treated.

For a 30% observed ORR rate and a sample size of N=30 yields an exact confidence interval of [0.15, 0.49]. These design parameters ensure a lower bound higher than 15%.

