1.3 Objectives(s)

1.3.1 Primary Objectives

- 1.3.1.1 EPd Cohort:
- To estimate the PFS in patients with MM treated by EPd as second- or third-line regimen after relapse or being refractory or intolerant to a prior lenalidomide-based regimen.

1.3.1.2 EN Cohort:

• To estimate the ORR.

Revised Protocol No.: 03 Date: 08-Mar-2018

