8.4.2 Efficacy Analyses

The efficacy endpoints, PFS and ORR, will be defined using the IMWG criteria. Responses will be assessed at every treatment cycle using central laboratory test results on myeloma urine and serum, local laboratory bone marrow aspiration test, and if needed bone marrow and skeletal survey results and CT/MRI assessments. Objective responses will include stringent complete

```
Revised Protocol No.: 03
Date: 08-Mar-2018
```

response, complete response, very good partial response and partial responses. The ORR and its 95% confidence interval (CI) using the Clopper-Pearson estimation procedure will be reported. PFS and OS will be plotted using Kaplan-Meier estimates, and if estimable, median and its 95% CI will be reported. Time to response will be analyzed for responders only with summary statistics provided. Duration of response will be reported using K-M estimates. The time to event responses will be recorded from the first day of the first cycle to the day that an event occurs. If no event occurs by the time the study is completed, the patient is censored for that event at the last day of subject contact.

For EPd cohort, the primary analysis of PFS will be conducted when 48 progression events have been observed.

For EN cohort, the primary analyses for ORR will be conducted when enrollment in the EN cohort is complete and all enrolled patients treated with the combination have received at least 3 cycles of treatment.

MRD negativity status for subjects in the EN Cohort will be evaluated by time points. The frequency of the MRD negativity status and the best MRD negativity status will be summarized for the EN cohort. The cross tabulation of the MRD negativity status and BOR will be presented. Summary statistics of the MRD levels and their corresponding percent changes from baseline will be tabulated by planned study day for the EN cohort. Potential association between the first/best MRD negativity status with PFS and OS will be evaluated in all treated patients. Additional details will be presented in the Statistical Analysis Plan.

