7.5.3 Objective Response

The other secondary objective of this study is to estimate the Objective Response Rate (ORR). The number and percentage of subjects in each category of best overall response (stringent CR [sCR], complete response [CR], very good partial response [VGPR], partial response [PR], minor (minimal response) [MR], stable disease/no change [SD], progressive disease [PD], or unable to determine [UD]) will be presented. An estimate of the objective response rate and an associated exact two-sided 95% CIs (Clopper and Pearson¹⁸) will be presented. Also, the number and percentage of subjects in each category of best overall response according to the investigator tumor assessment will be presented.

Analyses of ORR will be conducted based on the all treated analysis population, and also by subgroups based on lines of prior therapy (2L, 3L), or by age group (<65 years, \geq 65 years), and (<75 years, \geq 75 years). Subgroup analysis by ECOG PS (0-1,2), by response to most recent line of therapy (relapsed and refractory, relapsed, refractory, intolerant) and by ISS stage (I,II,III) if albumin and beta 2 microglobulin data are available will be conducted as well.

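### EN cohort: 9 responders in 30 gives an exact 95% lower bound of 14.7%, so the claim of a bound above 15% is untrue

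*Protocol*

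**What the plan says.** Protocol 8.1.2 plans about 30 treated subjects in the EN cohort, with 30 as the minimum: "The planned sample size will be approximately 30 treated subjects; screening will continue until a minimum of 30 patients are enrolled and treated". The precision statement starts from this case: "For a 30% observed ORR rate and a sample size of N=30". It gives the exact interval as [0.15, 0.49] and continues: "These design parameters ensure a lower bound higher than 15" per cent. The Synopsis and SAP 5.2 make the same statement.

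The interval method is fixed elsewhere. For the ORR, Protocol 8.4.2 says "95% confidence interval (CI) using the Clopper-Pearson estimation procedure will be reported". SAP 7.5.3 plans "an associated exact two-sided 95% CIs" and cites Clopper and Pearson. The EN primary objective in Protocol 1.3.1.2 is estimation: "To estimate the ORR".

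**The concern.** The printed lower limit is 0.15, and the next sentence says the bound is higher than 15%. Even at face value, 0.15 is not higher than 15%, so the claim can hold only if the unrounded limit lies above 0.15. It could equally lie below it and have been rounded up.

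If it lies below, then 9 responders out of 30 would not exclude a 15% response rate by the planned interval, although a reader of the protocol would think that it did. ORR is the primary endpoint of this cohort. In the published text, this interval and the sentence after it are the only quantitative support for N = 30. The EPd cohort, by contrast, has a hypothesised effect, a power figure and an expected event count.

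**Working it through.** **Inputs**

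- Responders x = 9 and n = 30, that is, 30% of 30 (Protocol 8.1.2).
- Two-sided 95% Clopper-Pearson interval (Protocol 8.4.2, SAP 7.5.3).
- Figures to check: the interval [0.15, 0.49], and a lower bound above 15% (Protocol 8.1.2).

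**Step 1. Reproduce the printed interval.** The Clopper-Pearson limits are beta quantiles:

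- lower = 0.025 quantile of Beta(x, n − x + 1) = Beta(9, 22) = 0.1473
- upper = 0.975 quantile of Beta(x + 1, n − x) = Beta(10, 21) = 0.4940

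To two decimals this is [0.15, 0.49]. The printed interval is reproduced.

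**Step 2. Compare the unrounded limit with 15%.** 0.1473 is below 0.15. The shortfall is 15.00 − 14.73 = 0.27 percentage points.

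**Step 3. Cross-check with the binomial tail.** The lower limit exceeds 0.15 only if P(X ≥ x | n = 30, p = 0.15) is below 0.025.

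- P(X ≥ 9) = 0.0278, which is above 0.025, so 15% lies inside the interval for 9/30.
- P(X ≥ 10) = 0.0097, which is below 0.025, so 15% lies outside the interval for 10/30.

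**Step 4. Neighbouring counts at n = 30**

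| Responders | Observed ORR | Exact 95% CI |
|---|---|---|
| 8/30 | 26.7% | 12.3% to 45.9% |
| 9/30 | 30.0% | 14.7% to 49.4% |
| 10/30 | 33.3% | 17.3% to 52.8% |

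**Step 5. Could another method have been meant?** For 9/30:

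| Method | Lower limit | Upper limit |
|---|---|---|
| Clopper-Pearson, 95% | 0.147 | 0.494 |
| Wilson, 95% | 0.167 | 0.479 |
| Agresti-Coull, 95% | 0.165 | 0.480 |
| Jeffreys, 95% | 0.160 | 0.477 |
| Mid-p, 95% | 0.157 | 0.480 |
| Blaker, 95% | 0.158 | 0.483 |
| Wald, 95% | 0.136 | 0.464 |
| Clopper-Pearson, 90% two-sided | 0.166 | 0.465 |

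Several of these put the lower limit above 15%, but none of them gives an upper limit of 0.49. Only the pre-specified 95% Clopper-Pearson interval matches both printed limits, and its lower limit is below 15%.

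**The case against.** The strongest reply is about weight, since the arithmetic is not in dispute. The printed interval is right at its printed precision, the miss is 0.27 percentage points, and the sentence feeds into nothing: no null rate, success boundary or go/no-go rule at 15% appears in the text, and the ORR will be reported with its exact interval whatever was said at planning. All of that stands, and it limits the consequence. It does not make the sentence true.

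A second reply is that 30 is a minimum, and slightly larger cohorts with an observed rate near 30% do clear the mark: 10/33 (30.3%) gives 15.6% and 10/34 (29.4%) gives 15.1%. This shows that the miss is narrow. But the claim is made for N = 30, and a larger cohort does not guarantee it either: 9/31 (29.0%) gives 14.2%.

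Third, *ensure* can fairly be read as conditional on the 30% and N = 30 named just before it. On that reading the sentence still fails, at 14.7%. On an unconditional reading it is weaker still, because the observed count is not a design parameter.

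Fourth, parts of the protocol are missing from the public copy, including the background section and the rationale cells in the summary of changes, so a further sizing rationale cannot be excluded. That is fair. The remark about the only quantitative support applies to the published text alone.

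**Conclusion.** The concern holds. With 9 responders among 30 treated subjects, the planned exact 95% interval is [0.147, 0.494], and its lower bound is 0.27 percentage points below the 15% that the plan says it exceeds. Ten responders are the fewest out of 30 that give a lower bound above 15%. The conclusion rests only on the plan's own inputs: 30% observed, N = 30, two-sided 95% Clopper-Pearson.

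This is a false statement of precision for the EN primary endpoint, made in three places, and it should be corrected. It is not a flaw in the analysis: no test, decision rule, sample size or result depends on it. If 9/30 were observed, however, the reported interval would openly contradict the protocol and SAP.

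**What to change.** In the Synopsis, Protocol 8.1.2 and SAP 5.2, delete the sentence about the lower bound and print the interval to three decimals as [0.147, 0.494].

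If the sponsor wants to keep a reference to 15%, the sentence could be replaced by:

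> With 9/30 responders the exact 95% CI is [0.147, 0.494]; at least 10/30 responders (33.3%, CI [0.173, 0.528]) are needed for a lower bound above 15%.

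Deletion is the cleaner choice if there is a risk that 10/30 would be read as a success criterion, since the cohort has none.

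The cost is a one-sentence text correction in three places. The stated precision becomes slightly less favourable. The sample size and the planned analysis stay as they are.

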8.2 Populations for Analyses

- The safety analysis set consists of subjects who receive at least one dose of study drug. The safety analysis set is also the all treated analysis set.
- The efficacy analysis set is the same as the all treated analysis set.

8.3 Endpoints

8.3.1 Primary Endpoint(s)

8.3.1.1 EPd Cohort

PFS is defined as the time from first dosing date to the date of the first documented progression per IMWG uniform criteria or death due to any cause, whichever occurs first. Subjects who die without a reported prior progression will be considered to have progressed on the date of their death. Subjects who did not progress or die will be censored on the date of their last evaluable assessment. Subjects who did not have any on study efficacy assessments and did not die will be censored on the first dosing date.

Subjects who switched to subsequent therapy prior to documented progression will be censored on the date of the last evaluable assessment prior to the initiation of the new therapy.

8.3.1.2 EN Cohort

ORR is defined as proportion of subjects with best overall response of partial response (PR) or better. Response will be determined per IMWG uniform criteria.

8.3.2 Secondary Endpoint(s)

8.3.2.1 EPd Cohort

- ORR is defined as proportion of subjects with a best overall response of partial response (PR) or better.
- OS is defined as the time from first dosing date to the date of death from any cause. A subject who has not died will be censored at last known date alive.

8.3.2.2 EN Cohort

- PFS definition: See Section 8.3.1.1
- OS is defined as the time from first dosing date to the date of death from any cause. A subject who has not died will be censored at last known date alive.

I	
I	

8.4 Analyses

8.4.1 Demographics and Baseline Characteristics

The demographic and baseline characteristics of patients in the safety analysis set will be presented. Among the baseline clinical characteristics are patients' ECOG Performance Status, baseline laboratory assessment for safety and efficacy endpoints, number of prior lines of therapy and types of previous therapy (Appendix 1), and disease status/stage (Appendix 5) at entry.

8.4.2 Efficacy Analyses

The efficacy endpoints, PFS and ORR, will be defined using the IMWG criteria. Responses will be assessed at every treatment cycle using central laboratory test results on myeloma urine and serum, local laboratory bone marrow aspiration test, and if needed bone marrow and skeletal survey results and CT/MRI assessments. Objective responses will include stringent complete

```
Revised Protocol No.: 03
Date: 08-Mar-2018
```

response, complete response, very good partial response and partial responses. The ORR and its 95% confidence interval (CI) using the Clopper-Pearson estimation procedure will be reported. PFS and OS will be plotted using Kaplan-Meier estimates, and if estimable, median and its 95% CI will be reported. Time to response will be analyzed for responders only with summary statistics provided. Duration of response will be reported using K-M estimates. The time to event responses will be recorded from the first day of the first cycle to the day that an event occurs. If no event occurs by the time the study is completed, the patient is censored for that event at the last day of subject contact.

For EPd cohort, the primary analysis of PFS will be conducted when 48 progression events have been observed.

For EN cohort, the primary analyses for ORR will be conducted when enrollment in the EN cohort is complete and all enrolled patients treated with the combination have received at least 3 cycles of treatment.

MRD negativity status for subjects in the EN Cohort will be evaluated by time points. The frequency of the MRD negativity status and the best MRD negativity status will be summarized for the EN cohort. The cross tabulation of the MRD negativity status and BOR will be presented. Summary statistics of the MRD levels and their corresponding percent changes from baseline will be tabulated by planned study day for the EN cohort. Potential association between the first/best MRD negativity status with PFS and OS will be evaluated in all treated patients. Additional details will be presented in the Statistical Analysis Plan.

8.4.3 Safety Analyses

Safety assessments will be performed prior, during and between dosing, and up to 100 days after the last treatment for the EN cohort and 60 days after the last dose in the EPd cohort and for subjects in the EN cohort who cross-over to the EPd cohort but discontinue treatment within 2 cycles of EPd treatment safety assessments will be performed up to 100 days after the last dose of nivolumab. The frequency, severity, relationship to combination of drug treatment, seriousness, and outcomes of adverse events (AEs) will be reported for the full safety analysis set. AE severity will be graded according to the NCI Common Terminology Criteria for Adverse Events 3.0. Results of targeted physical examinations prior to each dosing cycle will be presented.

Summary statistics on vital signs at screening, pre-infusion, 30 minutes after the start of infusion, at end of infusion and 30 minutes after the completion of infusion will be reported for each dosing cycle. Concomitant medications, SAEs, laboratory parameters, and performance status prior to dosing will be presented. The safety analysis set will be used for reporting safety /adverse events.

Revised Protocol No.: 03 Date: 08-Mar-2018

8.4.6 Outcomes Research Analyses (both cohorts)

Not applicable.

8.5 Interim Analyses

Administrative interim analyses may be performed at several times prior to completion of the study in order to facilitate program decisions and to support presentations or publications.

9. STUDY MANAGEMENT

9.1 Compliance

9.1.1 Compliance with the Protocol and Protocol Revisions

The study shall be conducted as described in this approved protocol. All revisions to the protocol must be discussed with, and be prepared by, BMS. The investigator should not implement any deviation or change to the protocol without prior review and documented approval/favorable opinion from the IRB/IEC of an amendment, except where necessary to eliminate an immediate hazard(s) to study subjects.

If a deviation or change to a protocol is implemented to eliminate an immediate hazard(s) prior to obtaining IRB/IEC approval/favorable opinion, as soon as possible the deviation or change will be submitted to:

- IRB/IEC for review and approval/favorable opinion
- BMS
- Regulatory Authority(ies), if required by local regulations

Documentation of approval signed by the chairperson or designee of the IRB(s)/IEC(s) must be sent to BMS.

If an amendment substantially alters the study design or increases the potential risk to the subject: (1) the consent form must be revised and submitted to the IRB(s)/IEC(s) for review and approval/favorable opinion; (2) the revised form must be used to obtain consent from subjects currently enrolled in the study if they are affected by the amendment; and (3) the new form must be used to obtain consent from new subjects prior to enrollment.

If the revision is done via an administrative letter, investigators must inform their IRB(s)/IEC(s).

9.1.2 Monitoring

BMS representatives will review data centrally to identify potential issues to determine a schedule of on-site visits for targeted review of study records.

Representatives of BMS must be allowed to visit all study site locations periodically to assess the data quality and study integrity. On site they will review study records and directly compare them with source documents, discuss the conduct of the study with the investigator, and verify that the facilities remain acceptable. Certain CRF/eCRF pages and/or electronic files may serve as the source documents.

In addition, the study may be evaluated by BMS internal auditors and government inspectors who must be allowed access to CRF/eCRFs, source documents, other study files, and study facilities. BMS audit reports will be kept confidential.

The investigator must notify BMS promptly of any inspections scheduled by regulatory authorities, and promptly forward copies of inspection reports to BMS.

9.1.2.1 Source Documentation

The Investigator is responsible for ensuring that the source data are accurate, legible, contemporaneous, original and attributable, whether the data are hand-written on paper or entered electronically. If source data are created (first entered), modified, maintained, archived, retrieved, or transmitted electronically via computerized systems (and/or any other kind of electronic devices) as part of regulated clinical trial activities, such systems must be compliant with all applicable laws and regulations governing use of electronic medical/health records (EMRs/EHRs), adverse event tracking/reporting, protocol required assessments, and/or drug accountability records).

When paper records from such systems are used in place of electronic format to perform regulated activities, such paper records should be certified copies. A certified copy consists of a copy of original information that has been verified, as indicated by a dated signature, as an exact copy having all of the same attributes and information as the original.

9.1.3 Investigational Site Training

Bristol-Myers Squibb will provide quality investigational staff training prior to study initiation. Training topics will include but are not limited to: GCP, AE reporting, study details and procedure, electronic CRF/eCRFs, study documentation, informed consent, and enrollment of WOCBP.

9.2 Records

9.2.1 Records Retention

The investigator must retain all study records and source documents for the maximum period required by applicable regulations and guidelines, or institution procedures, or for the period specified by BMS, whichever is longer. The investigator must contact BMS prior to destroying any records associated with the study.

BMS will notify the investigator when the study records are no longer needed.

If the investigator withdraws from the study (eg, relocation, retirement), the records shall be transferred to a mutually agreed upon designee (eg, another investigator, IRB). Notice of such transfer will be given in writing to BMS.

